Actual duration of intensive care unit (ICU) stay (hours) [duration]	
For subjects in Cohort 1: total number of hours of actual ICU stay experienced by a subject from first dose of study drug until end of study (sum of the duration of individual ICU records captured in the Hospitalization [Inpatient] eCRF) and is derived as:
 
time hours = sum [(end date/time – start date/time [of encounter])]/3600
 
Derivation and imputation rules: as for 'Duration of need for intensive care unit (ICU) stay (hours)'

Table 20: Additional Clinical Course Parameters for Hospitalized Subjects

Need for ICU stay [binary]	
Was there a medical need for the subject to stay in the ICU after first dose of study drug? Categories will be Yes (1) or No (0).
 
Only derive this parameter for subjects that were not in ICU before first dose of study drug (no score will be assigned otherwise).

Duration of oxygen supplementation [duration]	
The total number of hours a subject used supplemental oxygen (=event) from first dose of study drug until study termination, calculated as sum of [(end date/time of event - start date/time of event)/3600], rounded to one decimal for all separate events per subject
 
Derivation and imputation rules: as for 'Duration of need for intensive care unit (ICU) stay (hours)'
 
If the subject required oxygen supplementation prior to the current respiratory infection, the end date/time will be the date/time that the supplemental oxygen administration returned to the level provided prior to the current respiratory infection.

Need for oxygen supplementation [binary]	
Does the subject require any oxygen supplementation (non-invasive or invasive) after first dose of study drug?
 
Categories will be Yes (1) or No (0).
 
Only derive this parameter for subjects that did not require oxygen supplementation before first dose of study drug (no score will be assigned otherwise).
 
If the subject required supplemental oxygen prior to the current respiratory infection, requirement will be defined as having not returned to the level provided prior to the current respiratory infection.

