Requirement for non-invasive non-mechanical ventilation support [binary]	
Does the subject require non-invasive non-mechanical ventilation support after first dose of study drug? On the Oxygen Supplementation form, oxygen supplementation is indicated but the type of supplemental oxygen administration does not equal “Non-Invasive Mechanical Ventilation” or “Invasive Mechanical Ventilation”?
 
Categories will be Yes (1) or No (0).
 
Only derive this parameter for subjects that did not require non-invasive non-mechanical ventilation before first dose of study drug (no score will be assigned otherwise).

Requirement for non-invasive mechanical ventilation support [binary]	
Does the subject require non-invasive mechanical ventilation support after first dose of study drug, as indicated on the Oxygen Supplementation form: type of supplemental oxygen administration equals “Non-Invasive Mechanical Ventilation”?
 
Categories will be Yes (1) or No (0).
 
Only derive this parameter for subjects that did not require non-invasive mechanical ventilation support or invasive mechanical

Table 20: Additional Clinical Course Parameters for Hospitalized Subjects

	ventilation support before first dose of study drug (no score will be assigned otherwise).
Requirement for invasive mechanical ventilation support [binary]	Does the subject require invasive mechanical ventilation support after first dose of study drug, as indicated on the Oxygen Supplementation form: type of supplemental oxygen administration equals “Invasive Mechanical Ventilation”? Categories will be Yes (1) or No (0). Only derive this parameter for subjects that did not require invasive mechanical ventilation support before first dose of study drug (no score will be assigned otherwise).
Requirement for supplemental feeding/hydration [binary]	Does the subject require supplemental feeding/hydration (e.g. IV catheter/nasogastric tube) after first dose of study drug? Categories will be Yes (1) or No (0). Only derive this parameter for subjects that didn't require supplemental feeding/hydration before first dose of study drug (no score will be assigned otherwise). If the subject required supplemental feeding/hydration prior to the current respiratory infection, requirement will be defined as having not returned to the level provided prior to the current respiratory infection.

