The proportion (number [n] and percentage [%]) of subjects will be presented as frequency tabulation:

- Re-hospitalized (any reason): percentage (%) based on total number of hospitalized subjects in ITT-i analysis set and treatment group
- Re-hospitalized:
 - Adverse event:
 - Respiratory AEs:
 - ◆ RSV-related complications: modified definition as detailed in Section 5.4
 - ◆ Other respiratory AEs
 - Non-respiratory AEs
 - Other

In addition, the main reason(s) for re-hospitalization will be summarized descriptively.

Individual subject profiles will be provided for all subjects re-hospitalized.

Time to Discharge Since Hospital Admission, Time to Clinical Stability: Investigator Assessment Since Hospital Admission

These time to event variables will be analyzed using Kaplan-Meier analysis. Both the 80% and 95% 2-sided confidence intervals will be presented.

The aforementioned will be presented overall by treatment group and by the subgroups as defined in Section 2.4.

Need for ICU Stay, Need for Oxygen Supplementation, Requirement for Supplemental Feeding/Hydration

With reference to the definitions and derivations detailed in Section 5.3.1.3.2, summary includes those subjects not requiring the level of care/support at date/time of first dose of study drug.

The proportion (number [n] and percentage [%]) of subjects with data available will be presented, as frequency tabulation, by treatment group. Additionally, 95% 2-sided confidence interval for each binomial proportion within the individual categories will be presented as based on the Wilson score test.

Based on the categorization (Yes vs No), the difference in proportions between each active treatment group as compared to placebo will be investigated. Frequency procedure in SAS® provides Newcombe confidence limits with Mantel-Haenszel weights for the common risk difference (difference in proportion), controlling for the two randomization stratification factors (separately). The difference in proportion of 'Yes' for any ICU/supplementation need and both 80% and 95% 2-sided confidence intervals for this point estimate, controlling for randomization stratification factors (derived), will be presented.

Derived duration will be summarized descriptively only.

The aforementioned will be presented overall by treatment group and by the subgroups as defined in Section 2.4.

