Requirement for Non-invasive Non-mechanical Ventilation Support, Requirement for Non-invasive Mechanical Ventilation Support, Requirement for Invasive Mechanical Ventilation Support

These need for/requirement parameters will be summarized in similar manner as described above and will only be calculated for those subjects that do not require ICU stay or supplemental support (depending on the parameter of interest) before the first dose of study drug.

Time (hours) to End of Oxygen Supplementation, Time (hours) to End of Hydration/Feeding Supplementation, Time (hours) to End of Supplementation (up to 72h from first hospital discharge)

These time to event variables will be analyzed using Kaplan-Meier analysis. Both the 80% and 95% 2-sided confidence intervals will be presented.

The aforementioned will be presented overall by treatment group and by the subgroups as defined in Section 2.4.

In addition, time (hours) to end of oxygen supplementation (up to 72h from first hospital discharge), difference in median time (hours) to event between each active treatment group as compared to placebo will be investigated using the AFT model with log-logistic distribution. The model will include class variables treatment group with placebo as reference and randomization stratification factors (derived). Summary will include parameter estimates and associated standard error, covariance matrix of parameter estimates, estimated accelerated failure time ratio (as compared to placebo) and both 80% and 95% 2-sided confidence intervals.

The aforementioned will be presented overall by treatment group and by the subgroups as defined in Section 2.4.

Graphical presentation will include:

- Overlay of survival curves with Kaplan-Meier survival function and AFT on one plot

- Forest plot of accelerated failure time ratios and resulting confidence intervals for subgroups of interest as defined in Section 2.4 including the relevant subgroup variable as covariate in the model with subgroup*treatment group interaction.

Time to Return to Pre-RSV Disease Level for Respiratory Rate, Time to Return to Pre-RSV Disease Level for Heart Rate, Time to SpO2>92% on Room Air, Time to SpO2>95% on Room Air

These time to event variables will be analyzed using Kaplan-Meier analysis. Both the 80% and 95% 2-sided CIs will be presented.

The aforementioned will be presented overall by treatment group and by the subgroups as defined in Section 2.4.

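### The non-mechanical support row of SAP Table 20 does not exclude children already on mechanical ventilation, so weaning to mask or cannula can score as a new requirement

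*SAP*

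**What the plan says.** Table 20 in SAP Section 5.3.1.3.2 defines a set of binary need parameters for hospitalized subjects. Each has an event after first dose and a rule on who is scored.

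- **Non-invasive non-mechanical support.** The event is Yes (1) when "oxygen supplementation is indicated but the type of supplemental oxygen administration does not equal" either of the two mechanical types. The scoring rule is "Only derive this parameter for subjects that did not require non-invasive non-mechanical ventilation before first dose of study drug".
- **Non-invasive mechanical support (next row).** The scoring rule is "Only derive this parameter for subjects that did not require non-invasive mechanical ventilation support or invasive mechanical" ventilation support before first dose. It names its own level and the one above.
- **Need for oxygen supplementation.** The scoring rule is "Only derive this parameter for subjects that did not require oxygen supplementation before first dose of study drug", where oxygen covers non-invasive and invasive forms.
- **Need for ICU stay.** The event is medical need; the scoring rule is "Only derive this parameter for subjects that were not in ICU before first dose of study drug".

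Section 5.3.2.3.2 gives the analysis. For ICU stay, oxygen and feeding/hydration, the "summary includes those subjects not requiring the level of care/support at date/time of first dose of study drug". For the three ventilation parameters a separate paragraph limits the calculation to "subjects that do not require ICU stay or supplemental support (depending on the parameter of interest) before the first dose of study drug". The effect reported is "The difference in proportion of 'Yes' for any ICU/supplementation need", as a stratified difference from placebo with 80% and 95% intervals.

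**The concern.** Yes is the unfavourable category in all these rows, so each scored group should contain only children for whom a Yes means getting worse. The levels are ordered: no support, non-mechanical oxygen, non-invasive mechanical, invasive mechanical. A child who starts above a level can reach it only by improving. The non-invasive mechanical row takes account of this and the non-mechanical row does not. A ventilated child can therefore enter the scored group and be counted as a new requirement on coming off the ventilator. The proportion then mixes deterioration with recovery, and the difference from placebo can go against an arm in which more such children are weaned.

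**Working it through.** The SAP gives no figure to reproduce here. The check applies the Table 20 rules as written to the possible courses, then adds a simple illustration.

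**Rules applied**
- Non-mechanical row: no score if non-mechanical support was required before first dose; otherwise 1 if it is recorded afterwards.
- Non-invasive mechanical row: no score if either mechanical type was required before first dose; otherwise 1 if the non-invasive type is recorded afterwards.
- Need for oxygen row: no score if any oxygen was required before first dose; otherwise 1 if any is recorded afterwards.
- Aligned rule: the non-mechanical row, with no score also for either mechanical type before first dose.

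| Before first dose | After first dose | Non-mechanical row | Non-invasive mechanical row | Need for oxygen row | Aligned rule |
|---|---|---|---|---|---|
| Invasive only | Invasive, then nasal oxygen | **1** | no score | no score | no score |
| Non-invasive mechanical only | Same, then nasal oxygen | **1** | no score | no score | no score |
| Invasive only | Invasive throughout | **0** | no score | no score | no score |
| Invasive only | Invasive, then non-invasive mechanical | **0** | no score | no score | no score |
| Nasal oxygen, then invasive | Invasive, then nasal oxygen | no score | no score | no score | no score |
| None | Nasal oxygen | 1 | 0 | 1 | 1 |
| None | None | 0 | 0 | 0 | 0 |

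In the first four courses the non-mechanical row gives a score where the other two rows give none. The weaned child scores worse than the child who stays ventilated. The aligned rule removes these four courses and leaves children without prior support unchanged.

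**Illustration.** The arm size of 48 is the Cohort 1 target (SAP Section 1.4). All else is assumed: *b* children per arm unscored because of prior non-mechanical oxygen, *v* children per arm ventilated without it, and a 10% true new requirement among the remaining children in both arms. All *v* are weaned on active and none on placebo, which is the extreme case.

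- Active proportion = [0.10(48 − b − v) + v] / (48 − b)
- Placebo proportion = 0.10(48 − b − v) / (48 − b)
- Spurious difference = v / (48 − b)

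| b | v = 1 | v = 3 | v = 5 |
|---|---|---|---|
| 0 | 1/48 = 2.1 points | 3/48 = 6.25 points | 5/48 = 10.4 points |
| 24 | 1/24 = 4.2 points | 3/24 = 12.5 points | 5/24 = 20.8 points |

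Under the aligned rule the difference is 0 in every cell.

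**The case against.** The strongest reply is that the ventilation parameters have their own paragraph in Section 5.3.2.3.2, limited to "subjects that do not require ICU stay or supplemental support (depending on the parameter of interest) before the first dose of study drug". A ventilated child is on supplemental support, so the sentence can be read as excluding that child. This stands only in part. The bracketed qualifier sends the reader back to each parameter's own rule, and for this parameter that is the incomplete Table 20 row. If the sentence is meant to exclude all prior support, it conflicts with the row. The denominator is unclear on either reading.

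Four stronger readings are tempting and are not supported:

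- **That every ventilated child who is weaned is miscounted.** Table 20 excludes anyone who required non-mechanical support before first dose. A child who went from cannula to ventilator before dosing gets no score.
- **That the ventilation parameters carry two reference times.** The sentence about the date/time of first dose stands under the heading for ICU stay, oxygen and feeding/hydration. The ventilation paragraph says before first dose, as Table 20 does.
- **That a child who needs ICU care but is kept on the ward at first dose is counted as a new ICU need.** Table 20 alone, which goes by location, would allow this. Section 5 counts such a child as needing ICU, however, and Section 5.3.2.3.2 limits the ICU summary to children not requiring that level of care at first dose, which removes the child. What remains is a mismatch of wording between the two sections.
- **That a drug which helps weaning would look worse overall.** Need for oxygen supplementation excludes all prior oxygen, and the RSV Recovery Scale (Section 5.4) ranks mechanical ventilation below the ward categories, so a move from ventilator to ward counts as improvement there.

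**Conclusion.** The gap in the non-mechanical row is real and looks like a slip, since the neighbouring rows handle the same situation correctly. It affects children on mechanical ventilation at first dose with no earlier non-mechanical oxygen requirement. Its size cannot be stated: the SAP gives no baseline ventilation rate, and eligibility is left to the protocol, which is not at hand. A bias of a particular number of points therefore cannot be claimed; the illustration shows only that one weaned child counts for about 2 points in an arm of 48, or about 4 if half the arm is unscored. The SAP does allow for ventilation before dosing, because the two mechanical rows exclude it. The parameter is a secondary one, reported by estimation in Cohort 1 only. It is not a key clinical course endpoint and enters none of the interim decision rules in Section 5.6. It is worth correcting, but it does not threaten the trial's main conclusions.

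**What to change.** In the Table 20 row for non-invasive non-mechanical support, also assign no score to subjects who required non-invasive or invasive mechanical ventilation before first dose. Reword the ventilation paragraph of Section 5.3.2.3.2 so that it states this rule, or refers to Table 20 without the open qualifier.

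Separately, for need for ICU stay, need for oxygen supplementation and supplemental feeding/hydration, use one reference time in Table 20 and Section 5.3.2.3.2 (now before first dose in one, at first dose in the other). For ICU stay, also use one criterion (now location in one, level of care required in the other). Table 20 already takes start and end times of medical need from the ICU eCRF, so a rule based on need requires no new data.

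The cost is SAP wording, one added programming condition and a slightly smaller denominator for the non-mechanical parameter.

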 - time to age-adjusted normal values for otherwise healthy and to pre-RSV infection status for subjects with (a) risk factor(s) for severe RSV disease, for heart rate, respiratory rate, and/or blood oxygen level (i.e. without requirement of supplemental oxygen compared with pre-RSV infection status)
 - time to discharge (from initial admission and from initiation of treatment)
 - time to clinical stability, with clinical stability evaluated by the investigator (from initial admission and from initiation of treatment)
 - need for and duration of intensive care unit (ICU) stay; ‘need for ICU stay’ is defined as follows:
 - ◆ being admitted on the ICU (and ICU level of care is required)
 - ◆ being admitted on the hospital ward, with or without supplemental oxygen, but deemed to require ICU level of care (e.g. not transferred to ICU due to bed availability)
 - ◆ requiring ICU level of care is defined by some specific conditions:
 - acute or imminent respiratory failure
 - treatment of complicated acid-base or electrolyte imbalances
 - cardiogenic shock
 - acute congestive heart failure
 - hemodynamic instability
 - ◆ having other conditions requiring specialized equipment and/or staff competencies only available in the ICU
 - need for and duration of supplemental oxygen (regardless of method used); ‘need for supplemental oxygen’ is defined by:

- ◆ requiring invasive mechanical ventilation
- ◆ receiving any oxygen support requiring intubation or extracorporeal oxygenation
- ◆ receiving invasive mechanical ventilation
- ◆ receiving supplemental oxygen through a face mask or nasal cannula and not being able to sustain a blood oxygen saturation of $\geq 92\%$ when breathing room air for 15 minutes or less, tested once
- need for and duration of non-invasive ventilator support (e.g. continuous positive airway pressure) and/or invasive ventilator support (e.g. endotracheal-mechanical ventilation)
- need for hydration and/or feeding by IV administration or nasogastric tube; need for defined by $<50\%$ of normal oral intake
- time to clinical stability, defined as the time from initiation of study treatment until the time at which the following criteria are met:
 - ◆ return to age-adjusted normal values for otherwise healthy and pre-RSV infection status for subjects with (a) risk factor(s) for severe RSV disease, for all of the following signs/symptoms of RSV disease:
 - heart rate; AND
 - respiratory rate; AND
 - blood oxygen level

AND

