Time (hours) to clinical stability: investigator assessment since hospital admission [time to event]	
The time (hours) from hospital admission to first clinical stability (=event), as evaluated by the investigator and captured in the Clinical Stability eCRF.
 
Censoring rules and derivation: as for 'Time (hours) to hospital discharge'

Duration of need for intensive care unit (ICU) stay (hours) [duration]	
The total number of hours a subject experienced a medical need to stay in ICU (=event) from first dose of study drug until study termination, calculated as sum of [(end date/time of event – start date/time of event)/3600], rounded to one decimal for all separate events per subject as captured in the ICU eCRF. Based on the medical need to stay in ICU start/end date/time.
 
Where:
 
 • If the initial start date/time is prior to the first dose of study drug, the duration prior to the first dose of study drug will be deducted from the overall duration • If start date/time is missing, it will be imputed using date/time of first dose of study drug • If the end date is missing, the end date is considered to be after study completion or withdrawal • If the end date/time is after study completion/discontinuation, the duration after the date/time of study completion/discontinuation will be deducted from the overall duration (implies imputation of completion/discontinuation date/time) • If start date is available but the start time is not available, it will be imputed as 00:00 • If end date is available but end time is not available and: 
 ○ End date equals hospital discharge date, end time will be imputed as the hospital discharge time (only if hospital discharge time is also not an imputed time), else imputed as 23:59 (if hospital discharge time is also an imputed time) ○ End date does not equal hospital discharge date, end time will be imputed worst-case as 23:59

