Duration of supplemental hydration/feeding (hours) [duration]	Total number of hours of hydration/feeding support experienced from first dose of study drug until end of study (sum of the duration of individual hydration/feeding administration records captured in the Feeding/Supplemental Feeding eCRF) and is derived as: $\text{time hours} = \text{sum} [(\text{end date/time} - \text{start date/time}) \text{ [of encounter]}] / 3600$ Derivation and imputation rules: as for 'Duration of need for intensive care unit (ICU) stay (hours)'
Time (hours) to end of oxygen supplementation up to 72h from first hospital discharge [time to event]	Regardless of whether or not the subject is receiving oxygen supplementation at time of first dose of study drug: time (hours) from first dose of study drug to last end date/time of any oxygen supplementation received, but within 72h following first hospital discharge. Excludes oxygen supplementation received during re-hospitalizations that occurred >72 hours after initial hospital discharge Time (hours) will be set to 0h for subjects not requiring oxygen supplementation after first dose of study drug. Censoring will be applied as follows:

Situation**Censoring**

Table 20: Additional Clinical Course Parameters for Hospitalized Subjects

	
For subjects with missing data prior to event due to:
 
 • Completion • Withdrawal/early discontinuation of the study • Lost to follow-up (LTFU) 
Death (without previous evidence of supplementation end/hospital discharge)
	
Censored at date/time of completion, withdrawal/discontinuation of the study or LTFU accordingly Note: missing time will be imputed as 12:00
 
Censored at date/time of death
				
		time to event (hours) = (date/time of event or censoring – date/time of first dose of study drug)/3600, rounded to one decimal				

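### Table 20 adds up individual feeding/hydration records with no rule for overlap, so hours when two records run together are counted twice (minor; descriptive summaries only)

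*SAP*

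**What the plan says.** All of the following is in SAP Section 5.3.1.3.2, Table 20, unless another section is named.

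- **Feeding/hydration, target.** The quantity is introduced as "Total number of hours of hydration/feeding support experienced from first dose of study drug until end of study".
- **Feeding/hydration, derivation.** It is computed as the "sum of the duration of individual hydration/feeding administration records captured in the Feeding/Supplemental Feeding eCRF", with the formula sum of (end minus start).
- **Routes.** More than one route counts. The matching binary parameter refers to "supplemental feeding/hydration (e.g. IV catheter/nasogastric tube", and Section 5 lists "need for hydration and/or feeding by IV administration or nasogastric tube".
- **Oxygen.** The duration is "The total number of hours a subject used supplemental oxygen (=event) from first dose of study drug until study termination, calculated as sum of" end minus start, "rounded to one decimal for all separate events per subject".
- **Actual ICU stay.** This is likewise a sum over individual ICU records.
- **Imputation.** Feeding/hydration, oxygen and actual ICU stay all borrow the rules given for duration of need for ICU stay. A missing start date/time becomes the first dose, and a missing start time alone becomes 00:00. A missing end time becomes 23:59, unless the end date is the discharge date and a real discharge time exists. For a missing end date: "If the end date is missing, the end date is considered to be after study completion or withdrawal", after which time beyond study end is deducted.
- **Analysis.** Section 5.3.2.3.2 summarizes these durations descriptively only.

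**The concern.** Hours of support experienced is elapsed time: an hour on both a drip and a feeding tube is one hour of support. A sum of record lengths equals elapsed time only when no two records overlap. The SAP recognises two feeding/hydration routes that can run side by side, and neither the formula nor the imputation rules merge intervals. The only deductions, for time before first dose and after study end, are made record by record.

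The imputations widen the problem. They can turn sequential care into overlapping records after the data are captured, so clean clinical practice does not by itself prevent double counting.

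At stake are the means and spreads of a descriptive duration in the hospitalized cohort. A total longer than the child's time in the study would also be visibly wrong in a listing.

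**Working it through.** The SAP gives no numerical result for these durations, so there is no figure to reproduce. The check applies the written rule to assumed record patterns and compares it with elapsed time on support.

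**Inputs**
- Written rule: S = Σ(end − start) over records (Table 20).
- Elapsed time: U = length of the union of the record intervals.
- Study end: Day 28 ± 3 (Section 1.2). Day 28 is 27 × 24 = 648 h after first dose. The range is 24 × 24 = 576 h (Day 25) to 30 × 24 = 720 h (Day 31).
- Record patterns: assumptions, since the eCRF layout and data are not in the document.

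**Two records, general form.** S − U is the overlap, so the relative overstatement is overlap/U. It is 0% when the records are disjoint. It cannot exceed 100%, which is reached when both cover the same interval.

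**Concurrent routes**
- IV 0–72 h, tube 12–60 h: S = 72 + 48 = 120 h; U = 72 h; overstatement 48/72 = 67%.
- IV 0–48 h, tube 24–72 h: S = 48 + 48 = 96 h; U = 72 h; 24/72 = 33%.
- Both 0–72 h: S = 144 h; U = 72 h; 100%.
- Disjoint records 0–24 h and 48–72 h: S = U = 48 h; 0%.

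**Overlap created by imputation**
- *Missing times on a changeover day.* First dose is at 12:00 on Day 1. One record runs from first dose and ends on Day 2, end time missing, so it is set to 23:59 (about 36 h). The next starts on Day 2, start time missing, so it is set to 00:00 (12 h), and ends at 60 h. S ≈ 36 + 48 = 84 h; U = 60 h. About 24 h is counted twice although care may have been sequential.
- *Missing starts.* Two records with missing start date/time end at 24 h and 60 h; both are set to start at first dose. S = 24 + 60 = 84 h; U = 60 h.
- *Missing end dates.* Two records start at 0 h and 48 h; both run to Day 28. S = 648 + 600 = 1248 h; U = 648 h, which is all the time observable. With study end at Day 25 the figures are 576 + 528 = 1104 h against 576 h. At Day 31 they are 720 + 672 = 1392 h against 720 h.

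**Where it does not reach.** The three time-to-end-of-supplementation parameters in Table 20 use the last or maximum end date, so overlap cannot inflate them by addition. The durations are not among the key clinical endpoints (Section 5.2.3.2), the correlation endpoints (Section 5.5) or the interim decision rules (Section 5.6).

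**The case against.** Several points against the concern carry weight.

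- **The durations drive no inference.** Arms are compared on the need for support and on time to end of supplementation. This stands and keeps the point minor.
- **Frequency is unknown.** Double counting needs concurrent records held as separate rows, or missing dates or times. The eCRF might prevent some of this. This stands, and the percentages above show what the rule can do, not an expected bias. But the SAP invokes no such safeguard, and the imputations act after data capture.
- **The open-ended example owes much to the imputation itself.** One record without an end date already yields about 648 h. That is right; summing adds the further 600 h, which takes the total beyond the observable time.
- **Oxygen may already be correct.** Its rule sums separate events, with use of oxygen as the event, which can fairly be read as distinct episodes. The term is undefined, and two open-ended events would still overlap, but double counting of oxygen cannot be asserted from the text.

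A reader might also infer three stronger things:

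- *That a listed secondary endpoint is misderived for feeding/hydration.* Section 5 lists only the need for hydration/feeding. Duration is listed there for oxygen and ICU stay, while the feeding/hydration duration appears only in Table 20.
- *That the total depends on how many records a site opens.* It does not: splitting support into disjoint records leaves the sum unchanged.
- *That the error is greatest in the sickest children.* This is plausible, but no figure in the document supports it.

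**Conclusion.** The point holds, at minor severity. For supplemental hydration/feeding the written formula does not deliver the stated quantity when records overlap. For two modes the overstatement is 0% to 100% (67% in the first illustration). Once two records lack end dates the total can exceed the time observed. This rests on assumed record patterns and on records being able to overlap in the eCRF or after imputation.

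Actual ICU stay uses the same record sum and imputations, so the same wording should cover it, although the only mechanism visible there is missing dates or times. For oxygen the wording is ambiguous rather than wrong. The text does not support any wider claim about the trial's efficacy conclusions: the consequence stops at descriptive duration summaries.

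**What to change.** Add one rule to Table 20 covering the feeding/hydration, oxygen and ICU durations. First apply the date and time imputations and truncate each record to the period from first dose to study end. Then, within each support type, merge overlapping or contiguous records and sum the merged intervals. The total then cannot exceed the time observed. State also that separate oxygen events means the merged, non-overlapping episodes.

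The cost is a sentence or two in the SAP and a few lines of programming. No new data are needed, and results for subjects whose records do not overlap are unchanged.
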